#### **Safety Assessments:**

Safety will be assessed by the following:

Vital signs, 12-lead electrocardiograms, clinical laboratory evaluations (clinical chemistry, haematology and urinalysis), faecal occult blood tests and monitoring of AEs.

#### **Statistical Methodology:**

Descriptive summaries for safety data by regimen will be provided, including changes from baseline, as required.

Descriptive summaries for MRI assessments by regimen will be provided. The percentage and number of subjects with gastric retention at Days 2, 4, 7, 10 and 14, will be presented. Summary plots will also be provided.

Descriptive summaries will be provided for all PK concentration and parameter data by regimen, including plasma concentrations on Days 3 and/or 5 at all additional time points taken, if applicable.

Formal statistical analysis will be performed on the PK parameters AUC(0-t), AUC(0-168), AUC(0-inf) and Cmax to assess relative bioavailability. The PK parameters will undergo a natural logarithmic transformation and will be analysed using a mixed effects model with terms for regimen as a fixed effect and subject as a random effect. Adjusted geometric mean ratios (GMRs) and 90% confidence intervals for the GMR will be provided for each relevant comparison between MR prototype capsule formulations. In addition comparisons of formulations dosed in the fed and fasted state will be made, as appropriate.

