### 3 Synopsis

Sponsor: Lyndra Inc.	Investigational Medicinal Product: Memantine Hydrochloride Modified Release Prototype Capsule	EudraCT No.: 2017-000982-61
Title of Study:		
A Study Designed to Determine the Gastro-Retentive and Modified Release Properties of Memantine Hydrochloride Prototype Capsule Formulations in Healthy Subjects		
Principal Investigator:		
[name] MBChB, MRCS (Ed)		
Study Centre:		
Quotient Clinical, [name]		
Objectives:		
Primary:		

 
To assess the gastro-retentive (GR) properties of memantine hydrochloride modified release (MR) prototype capsules as determined by magnetic resonance imaging (MRI).
 
		
Secondary:		

 
To determine the pharmacokinetics (PK) of memantine hydrochloride when administered as the MR prototype capsules.
 
To provide additional safety and tolerability information for memantine hydrochloride MR prototype capsules.
 
To assess the impact of dosing in the fed state on the PK properties of a selected memantine hydrochloride MR prototype capsule (optional).
 
To assess the impact of dosing in the fed state on the GR properties of a selected memantine hydrochloride MR prototype capsule (optional).
 
		
Exploratory:		

 
To assess the impact of diurnal differences and food consumption on the PK of memantine hydrochloride MR prototype capsule(s) on Days 3 and/or 5 of selected regimen(s).
 
To use abdominal X-ray to confirm the elimination of the elastomeric core of the memantine hydrochloride MR prototype formulations from the body by Day 21 where the formulation contains radiopacifier.
 
		
Methodology:		
This is a single centre, open-label, single dose, 5-period study in 24 healthy male and female subjects, with an optional Period 6, if required. It is expected the study will be executed in 3 cohorts of 8 subjects, with each cohort participating in up to 2 study periods (total of up to 6 study periods). Cohort 3 may be conducted in parallel with Cohort 2.		
Subjects will be dosed in a sequential manner, as appropriate. Each subject will be administered up to 2 regimens across 2 study periods as follows:		

Cohort	Regimen	Investigational Medicinal Product Dose
1	A	50 mg Memantine Hydrochloride MR Prototype Capsule as Formulation 1

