	B	50 mg Memantine Hydrochloride MR Prototype Capsule as Formulation 2
2	C	50 mg Memantine Hydrochloride MR Prototype Capsule as Formulation 3
	D	50 mg Memantine Hydrochloride MR Prototype Capsule as Formulation 4
3	E	50 mg Memantine Hydrochloride MR Prototype Capsule as Formulation 5 or a previously dosed MR Prototype Capsule
	F (optional) a	50 mg Memantine Hydrochloride MR Prototype Capsule as Formulation 6 or a previously dosed MR Prototype Capsule

MR, modified release

a Regimen F will be administered to Cohort 3 in Period 2, if required, either in the fasted state or after a breakfast (meal composition to be confirmed [tbc])

Regimens A to E: planned dose administration will be in the fasted state following an overnight (minimum 10 h) fast; however, food status for Regimens B to E may be changed (e.g., administered with a meal composition [tbc]) based on emerging GR properties and PK data from previous regimens

Details of the IMP are provided in the IMP section

There will be a minimum 35-day interval between each dose administration. If at Day 14 of Period 1 plasma PK levels are >20 ng/mL, subjects will not progress to a second treatment period.

An interim decision will take place after each regimen to decide on the memantine hydrochloride MR prototype capsule to dose in the next regimen, prandial status and food composition for dose administration in the subsequent period, and after Regimen E to decide if Regimen F is required. Selection of the MR prototype capsule formulations will only be made after a complete review of all data collected from the previous cohort(s). For selection to occur, data must be available from a minimum of 6 subjects in each regimen who have completed the planned safety, PK and MRI assessments up to 312 h (Day 14). Where the desired GR properties have not been achieved for any dosed formulation the dose decision can select any previously tested formulation to dose again in the fed state during the next study period since it is known that dosing in the fed state can improve gastroretention of oral dosage forms. For all regimens, blood samples will be collected for PK analysis up to Day 35 and there will be the option to increase the number of PK samples over a 24-hour period on Days 3 and/or 5 to assess the impact of diurnal differences and food consumption during the regimen on the PK profile (details provided in [PK Assessments](#) section).

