**Pharmacokinetic Assessments:**

Venous blood samples for PK analysis will be collected at regular time intervals.

Up to an additional 10 PK samples may be taken over a 24-h period on Days 3 and/or 5 if the option is taken to assess the impact of diurnal differences and food consumption during the regimen on the PK profile (see [Study Design](#) section). During Regimen A of Cohort 1, these additional samples will be collected at 4-h intervals throughout Days 3 and/or 5. In subsequent cohorts and/or regimens, this schedule may be adjusted based on emerging PK data from previous regimens, subject to the restriction that up to 10 additional samples may be taken in total over a 24-h period on Days 3 and/or 5 for this purpose. If the MRI imaging on Days 2

and/or 4 shows that the MR prototype formulation is no longer resident in the stomach, the additional PK sampling will not be performed on the subsequent day.

The plasma concentration data for memantine, provided by York Bioanalytical Sciences, will be analysed by Quotient Clinical using Phoenix WinNonlin v6.3 or a more recent version (Certara USA, Inc., USA).

The following PK parameter estimates will be obtained, where possible and appropriate: Cmax, AUC(0-t), AUC(0-168) and AUC(0-inf).

Relative bioavailability (Frel) of the selected memantine hydrochloride MR prototype capsule in the fed state compared to the fasted state (if tested).

Additional PK parameters and/or comparisons may be calculated, which will be detailed in the Reporting and Analysis Plan (RAP).

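### Must the fed/fasted bioavailability comparison be tied to subjects who receive both food states, or separated from cross-cohort comparisons?

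*Combined protocol and SAP*

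**What the plan says.** All references are to section 3, Synopsis.

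- **Objectives.** The effect of fed dosing on the PK of one selected capsule is a secondary objective, marked optional.
- **Methodology.** There are three cohorts of 8, each with up to two periods, and each subject receives at most two regimens. The regimen table assigns A and B to Cohort 1, C and D to Cohort 2, and E and F to Cohort 3. Cohort 3 may overlap Cohort 2 in time. Regimen F may be "Formulation 6 or a previously dosed MR Prototype Capsule", and E has the parallel option with Formulation 5. The table note adds that "food status for Regimens B to E may be changed". The interim-decision text says that, where gastric retention falls short, "the dose decision can select any previously tested formulation to dose again in the fed state during the next study period".
- **Pharmacokinetic Assessments.** The food-effect estimate is named: "Relative bioavailability (Frel) of the selected memantine hydrochloride MR prototype capsule in the fed state compared to the fasted state (if tested"). Additional comparisons are left to the Reporting and Analysis Plan (RAP).
- **Statistical Methodology.** Log-transformed AUCs and Cmax are analysed "using a mixed effects model with terms for regimen as a fixed effect and subject as a random effect". Geometric mean ratios (GMRs) with 90% CIs "will be provided for each relevant comparison between MR prototype capsule formulations". The fed/fasted sentence follows: "In addition comparisons of formulations dosed in the fed and fasted state will be made, as appropriate".
- **Sample Size and Power.** No formal calculation was made. Adequacy is judged on at least 6 evaluable subjects per regimen.

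**The concern.** A food effect is usually estimated by giving the same people the same product in both states. Nothing here requires that. A capsule first given fasted in Cohort 1 could be given fed in Cohort 3, and the fed/fasted ratio would then compare different people, with cohort and food state changing together. Within a cohort the subjects are the same, but all take the regimens in the same order, so period and regimen change together. Because food status may also change for Regimens B to E, a ratio between two formulations could carry a food effect as well.

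The analysis text treats all these ratios alike, and the sample-size statement counts subjects per regimen, not subjects with both states. At stake is how a reader interprets the fed/fasted ratio: the same 6 to 8 subjects per regimen give much less information about food when the reference lies in another cohort.

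**Working it through.** **Plan's own figure.** 3 cohorts × 8 = 24 subjects, as stated. The plan gives no CV, power or precision figure to reproduce.

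**Pair counts (cohorts AB, CD, EF).**
- Re-dosing only at the table's slots: E against A to D gives 4 pairs and F against A to E gives 5, total 9. Only E-F lies within a cohort.
- Adding the interim-decision permission, so that B, C and D can also be fed re-doses: 6 × 5 / 2 = 15 pairs, of which A-B, C-D and E-F lie within a cohort.
- Both totals are maxima. If Cohort 3 runs alongside Cohort 2, C and D may not be available as references when E is chosen.

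**Precision under the planned model.** The CVs are assumptions: 20% within subjects, 30% to 50% between. Variance on the log scale is v = ln(1 + CV²), so v_w = 0.0392 and v_b = 0.0862 (30%) or 0.2231 (50%).
- Within-cohort SE = √(2v_w/n). For n = 8: √(2 × 0.0392/8) = 0.099, on 48 − 6 − 21 = 21 df.
- Cross-cohort SE = √(2(v_w + v_b)/n). For n = 8: 0.177 or 0.256, Satterthwaite df 28.5 or 24.4.
- A generalised least squares calculation for the full layout (3 cohorts × 8 subjects × 2 regimens, between-subject CV 30%) gives 0.099 for A-B, C-D and E-F and 0.177 for each of the other 12 pairs.

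| 90% CI factor, exp(t × SE) | Within cohort | Cross-cohort, CV_b 30% | Cross-cohort, CV_b 50% |
|---|---|---|---|
| n = 8 | ×/÷1.19 | ×/÷1.35 | ×/÷1.55 |
| n = 6 | ×/÷1.22 | ×/÷1.42 | ×/÷1.67 |

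At n = 8 the cross-cohort interval is 1.8 to 2.6 times as wide on the log scale. An 8-versus-8 cross-cohort contrast carries the information of 8v_w/(v_w + v_b) = 2.5 or 1.2 paired subjects.

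**Sensitivity.** The SE ratio is √(1 + v_b/v_w). It is 1.28 at within/between CVs of 25%/20% and 4.8 at 10%/50%, so the size of the loss is not known from the documents.

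**Validity of the interval.** With no cohort effect, simulated coverage of the cross-cohort 90% CI is 90%. It falls only if a cohort SD is assumed: 87% to 89% at 0.05 log units and 81% to 85% at 0.10. The documents give no such SD.

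**Could a model term help?** Six regimens fill the 3 × 2 = 6 cohort-by-period cells exactly. The Cohort 1 indicator is the sum of the A and B indicators, and the second-period indicator is the sum of B, D and F. With each regimen as its own level, fixed cohort and period terms add no rank to the model. The aliasing comes from the sequential design; it is not an omission from the model.

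**The case for a change.** The case for acting is that the Synopsis calls this a formal statistical analysis with 90% CIs and declares the sample size adequate for the objectives on a per-regimen count. A subject is evaluable after a single dose. Some subjects are barred from Period 2, and up to 4 per cohort may be replaced. Six evaluable subjects per regimen therefore do not guarantee six pairs, even for E-F. The fed/fasted ratio is already named, so leaving additional comparisons to the RAP does not clearly cover it. Listing the comparisons and their paired counts would cost only a few lines.

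These observations are correct, but they show less than they seem to:

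- The named fed/fasted ratio concerns one selected capsule in two states, so it cannot mix formulations. Mixing can arise only in the separate between-formulation ratios.
- Study Design plans A to E fasted and names optional Regimen F as the after-breakfast regimen. F follows E in the same cohort, so a paired comparison is available if both use the same capsule.
- The regimen table shows which pairs share a cohort, and a cross-cohort ratio has a visibly wider interval.
- A blanket within-subject label for within-cohort ratios could be wrong. If 4 of 8 subjects were replaced at Period 2, only 8 − 4 = 4 pairs would remain. The random subject term handles such partial pairing; a fixed label does not.
- The RAP is not among the documents, so it cannot be shown to be silent on these comparisons.

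What stands is a point of good reporting: give the number of subjects with both regimens and name what is confounded with each ratio.

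**Conclusion.** No change to the plan is needed. The design facts are right: no subject is required to receive one capsule in both states, and at most 3 of 15 pairs can be within-subject. But the planned model estimates every contrast and gives the cross-cohort ones a suitably wider interval, valid if cohorts are exchangeable. The loss of precision is real but of unknown size, about 1.3 to 4.8 times on the log scale over the assumed CVs. No added cohort or period term would remove the confounding. Requiring the food comparison to stay within one cohort would limit the interim choice of capsule, which serves the primary aim of gastric retention.

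The objective is secondary and optional, the study is exploratory, and the plan attaches no equivalence limit or decision rule to these intervals. Listing and labelling the comparisons would alter no estimate, interval or conclusion. This is a gap in detail that the analyst can be expected to fill in the RAP or the table footnotes, with actual paired counts and a note where food state differs between formulations. The conclusion would be different if a decision limit were set on the fed/fasted ratio.

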#### **Sample Size and Power:**

The study is exploratory and no formal sample size calculation was performed. For a study of this type, a sample size of 8 subjects enrolled in each cohort to achieve a minimum of 6 evaluable subjects per regimen is considered sufficient to meet the objectives of the study. A subject is considered to be an evaluable subject for the study if they have received one

dose of memantine hydrochloride MR prototype capsule and have PK data (AUC0-168) and safety data up to Day 8.
